The study implementation phase will be conducted at 30 HIV clinics located in Lagos, Nigeria. Sites and participants for the proposed study will be recruited from the list of over 67 HIV clinics registered with the Lagos State Healthcare Board. The NIMR will recruit 960 patients from 30 HIV clinics from this list under the guidance of Lagos State AIDS Control Agency, which funds comprehensive care for its HIV patient network in Lagos State. Note that this means recruitment of about 32 participants at each of the HIV clinics. Eligibility criteria for study participants are outlined below.

Inclusion criteria

- Be an adult aged 18 years and older.
- Attends one of the 30 HIV clinics.
- Have a diagnosis of HTN with uncontrolled blood pressure, i.e. BP is 140-179/90-100 mm Hg.
- Ability to provide consent.

Exclusion criteria

- BP>180/110 mm Hg;
- history of chronic kidney disease, heart disease, diabetes
- Stroke,
- pregnancy
- Inability to provide informed consent.
- Refusal to participate in the study.

Screen Failures

Screen failures will be referred to the PHCs for further management as is done in routine practice.

Strategies for Recruitment and Retention

The research staff will conduct the screening, consent, enrollment, and all study assessments. The study will recruit 30 HIV clinics from the network of 67 HIV clinics, who are part of the 100 primary care practices managed by the Lagos State Healthcare Board (LSPHB). All 67 HIV clinics are affiliated with the Lagos State AIDS Control Agency, which utilizes LSPHB to provide comprehensive primary care services to PLWH. Eligible HIV clinics will be selected from areas geographically distinct from one another. Once a clinic agrees to participate, their director will be asked to sign an MOU and identify 2 HIV nurses to be trained. Eligible patients will be identified from the HIV clinics during routine visits. Each clinic will recruit 32 patients using these inclusion criteria: 1) patient receiving care at the clinic; 2) adults 40 years and older; 3) BP 140-179/90-100 mm Hg; and 4) can provide informed consent. Exclusion criteria: 1) BP>180/110 mm Hg; history of chronic kidney disease, heart disease, diabetes or stroke, pregnancy; 2) inability to provide consent; and 3) refusal to participate.

SECTION 4: Study Intervention

Description of Study Intervention and its Administration

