Make recommendations to the NHLBI, IRB, and investigators concerning continuation or discontinuation of the trial(s).

Protect the confidentiality of the trial data and the results of monitoring by ensuring that computerized data files (quantitative and qualitative) are password protected. Any back-ups made of the computerized data will be put on separate hard drives which will also be password protected. Only named research staff will have access to the data onsite and offsite.

Implementation of the study protocol will be monitored by the study team in Nigeria, which comprises of the PI in Nigeria and the research staff (i.e. Research Coordinator, Research Assistant), who will be responsible for the monitoring and quality control of the study. The team meets bi-weekly to monitor the study progress, quality of data collection, adherence to the study manual/protocol, and good clinical practice. Study staff will be trained on all study procedures and documentation yearly. The study team will ensure that access to all forms and relevant documents is made available to members of the DSMB upon request, to facilitate their inputs or recommendations on how to improve study activities.

Study Procedure and Assessments

Study Procedures following randomization: After completion of the baseline data collection, all HIV clinics will be randomized in 5 cohorts of 6 clinics every 6 months for 30 months. Upon completion of recruitment of each cohort, the clinics are randomized in a 1:1 ratio to either the PF intervention group or the self-directed group. The randomization sequence will be generated by the study statistician and secured away from the clinics following CONSORT guidelines.

Study Visits: Eligible patients will be identified from the HIV clinics during routine visits. Once eligibility is confirmed, all patients regardless of their group assignment, will have a total of five study visits: baseline, 6, 12 months, 18 months, and 24 months post randomization. The structure of each study visit and the respective measures will be the same for each group (see study measures below). Beginning with the baseline visit, an average of 3 BP readings will be used as the measure for each study visit. The same procedure will be repeated at 6-, 12-, 18- and 24-month study visits.

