Follow-up Study Visits (6, 12, 18, and 24 months): The research coordinator (RC) will meet with each patient to collect follow up data on primary outcome measure (BP measurements identical to that described for the baseline visit) and secondary outcomes. Study measures for both groups are similar and will be conducted in the same manner by the RC. Patients in the HIV clinics randomized to the Self-Directed Group will attend follow up study visits as scheduled while those in the clinics randomized to the PF Intervention will meet with their nurses every three months [for lifestyle counseling and treatment] in addition to the scheduled study visits.

On-time Follow-up Study Visits (6, 12, 18, and 24 months): On-time visit occurs within a +/- 3-months window of the expected follow-up date. For the 6-month follow-up visit, an on-time visit occurs between 3 and 9 months after baseline visit. For the 12-month visit, an on-time visit occurs between 9 and 15 months. For the 18-month visit, an on-time visit occurs between 15 and 21 months.

Baseline visits: The RC will confirm eligibility status and obtain informed consent from each patient. At baseline, we will measure the organizational and individual-level factors shown to affect implementation of evidence-based practices, including leadership, organizational capacity to change, individual attitudes toward evidence-based practices, and the degree of buy-in among practice facilitators.

SECTION 6: Study Measures

Primary Outcome: Change in systolic BP from baseline to 12 months. The SBP reduction in patients will be assessed as mean change in systolic BP from baseline to 12 months.

Secondary Outcomes are:

Adoption [proportion of patients who were correctly diagnosed with HTN, received lifestyle counseling and antihypertensive treatment]; and *sustainability* [maintenance of TASSH uptake at the HIV clinics at 24 months].

The mediators of TASSH across the HIV clinics at 12 and 24 months.

Assessment of Outcome Measures:

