determined. A detailed analysis of the interviews should generate a conceptual model that elucidates barriers and facilitators of the uptake of TASSH within participating HIV clinics in Nigeria. It should also suggest modified facilitation strategies tailored to the clinics' context to overcome these challenges.

Analysis for Aim 2

Analysis for Aim 2 will consist of a repeated measures mixed-effects model for systolic BP (SBP), with fixed effects for time and intervention arm, and random effects for clinic. An interaction term be included for the intervention arm and time; this interaction, if non-zero, will indicate that the degree of change of SBP over time differs for those in the practice facilitation intervention compared to those in the self-directed condition. Also, for this aim assessments will include whether adjustment for any baseline characteristics is necessary, including such adjustments based on the change-in-estimate criteria.

Analysis for Aim 3

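### The Aim 2 model leaves each arm its own baseline SBP mean, so the primary estimate moves with chance baseline imbalance and gives up some precision that pre-specified baseline adjustment could recover

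*Combined protocol and SAP*

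**What the plan says.** Section 6 (Study Measures) defines the primary outcome: "The SBP reduction in patients will be assessed as mean change in systolic BP from baseline to 12 months".

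Statistical Considerations, Analysis for Aim 2, gives a mixed model for repeated SBP measurements with "fixed effects for time and intervention arm, and random effects for clinic. An interaction term be included for the intervention arm and time". A non-zero interaction is to be read as a difference between the arms in how SBP changes. On covariates it adds only that "assessments will include whether adjustment for any baseline characteristics is necessary, including such adjustments based on the change-in-estimate criteria". Baseline SBP is not named as a covariate. For this aim the text states no patient-level random effect or residual covariance, no coding of time, and no list of the visits that enter.

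On timing, Section 5 (Study Procedures following randomization) says: "After completion of the baseline data collection, all HIV clinics will be randomized in 5 cohorts of 6 clinics every 6 months for 30 months". The same section schedules visits at baseline, 6, 12, 18 and 24 months. Section 4 gives 15 clinics per arm, with randomisation stratified by cohort only. Section 3 gives 32 patients per clinic and 960 in total.

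**The concern.** Baseline SBP enters the model as an outcome, and the arm main effect lets its mean differ by arm. If baseline is collected before allocation, any arm difference at baseline is chance, and nothing in the cohort stratification balances it. The interaction subtracts the whole of that difference, although only part of it is expected to persist to 12 months. The primary estimate therefore depends on the draw of 15 clinics per arm, and its standard error can be larger than these data require.

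The covariate clause does not fill the gap. It does not name baseline SBP, and it makes adjustment depend on the data. Baseline SBP added as a main-effect covariate, with the same coefficient at both visits, would also cancel out of the interaction in complete data.

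**Working it through.** **Plan's own figure.** 30 clinics × 32 patients = 960, which agrees with the stated total. The documents give no effect size, SD, ICC, correlation or power, so no power calculation can be reproduced.

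**Set-up.** Let D0 and D12 be the arm differences in clinic-mean SBP at baseline and 12 months, each with variance v, and let r be the correlation of clinic means between the two visits. Any estimate of the form D12 − b·D0 has variance v(1 + b² − 2br).

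- Planned interaction, 0/12 data: b = 1, variance 2v(1 − r).
- Baseline-adjusted with correct covariance: b = r, variance v(1 − r²).
- Ratio, adjusted to planned: (1 − r²) / [2(1 − r)] = (1 + r)/2.
- Extra movement of the planned estimate per mmHg of baseline imbalance: 1 − r.

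In five simulated complete trials of 30 × 32, the planned interaction equalled the raw difference in change to three decimals, both with time coded 0/12 and with linear time over 0/6/12 (slope × 12).

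**Range of r (all inputs assumed).** Take ICC 0.01–0.10, clinic autocorrelation (CAC) 0.6–1.0 and patient autocorrelation (IAC) 0.3–0.7.

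r = [ICC·CAC + (1 − ICC)·IAC/32] / [ICC + (1 − ICC)/32]

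- Lowest: ICC 0.01, CAC 0.6, IAC 0.3: 0.01528/0.04094 = 0.37; ratio 0.69, a 31% reduction.
- Highest: ICC 0.10, CAC 1.0, IAC 0.7: 0.11969/0.12813 = 0.93; ratio 0.97, a 3% reduction.

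**Worked case.** ICC 0.02, CAC 0.8, IAC 0.5, SD 18 mmHg.

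- r = 0.03131/0.05063 = 0.62.
- v = (2/15) × 324 × 0.05063 = 2.19.
- Planned SE = √(2 × 2.19 × 0.38) = 1.29 mmHg.
- Adjusted SE = √[2.19 × (1 − 0.62²)] = 1.16 mmHg, ratio 0.81.
- Simulation gave a slope of the planned estimate on D0 of about −0.38, and about 0 for the adjusted one.
- A 3 mmHg imbalance moves the planned estimate by 3 × 0.38 = 1.1 mmHg.

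**With baseline truncated to 140–179.** Assume SD 15–20, mean 140–155 and visit correlation 0.5–0.7 before selection, ICC 0.01–0.05 and clinic-level correlation 0.3–0.6. Visit variances now differ. With B the covariance matrix of clinic means, the variances are (2/15)(B00 + B11 − 2B01) for change and (2/15)(B11 − B01²/B00) for adjusted.

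- Ratio 0.85–0.99, median about 0.93: a reduction of 1% to 15%.
- A 2-SE imbalance shifts the planned estimate by about 0.3–1.2 mmHg, against a planned SE of about 0.8–1.9 mmHg.

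**Constraint added to a clinic-only random effect.** The model then chooses b from a misspecified covariance. For ICC 0.01, CAC 1.0, IAC 0.7, r = 0.77 but the fitted b is about 0.41. The ratio to planned is (1 + 0.41² − 2 × 0.41 × 0.77) / (2 × 0.23) ≈ 1.18; a slightly different approximation gives 1.19. Over the grid the ratio runs from 0.69 to about 1.19.

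**Cost of estimating the slope from 30 clinics.** Standard covariance-adjustment theory with one covariate inflates the adjusted variance by 1 + 1/(30 − 4) = 1.038 on average. The net ratio (1 + r)/2 × 1.038 stays below 1 only if r is below about 0.93.

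**The case against.** Several objections stand in part.

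- **Change is the declared outcome and the planned estimator is unbiased.** This is correct. A reader might infer that the planned analysis is biased or invalid; it is not. The dependence on imbalance is conditional on the draw, and the rest is precision.
- **The interaction need not equal raw change.** Also correct. Visits and time coding are not stated. With linear time over all five visits the interaction is a slope difference, and with the attrition foreseen under missing data the equality is not exact. This is a further reason to name the 12-month contrast.
- **The entry range.** The criterion is "Have a diagnosis of HTN with uncontrolled blood pressure, i.e. BP is 140-179/90-100 mm Hg". A reader might infer that this restriction lowers the slope of 12-month on baseline SBP and so makes the problem worse. Selection on baseline leaves that slope unchanged: simulated slopes stayed at 0.50–0.70 before and after truncation. It shrinks baseline variance, which reduces the gain. Elsewhere uncontrolled BP is systolic or diastolic elevation, so it is also unclear whether analysed baseline SBP is truncated at all.
- **The remedy is not free or never worse.** A reader might infer that it is, because the data already exist. With the stated clinic-only random effect the constraint can cost up to about 19% in variance, and with very stable clinic means the gain can disappear in 30 clinics.
- **Timing.** Section 5 is explicit, but Section 4 says randomisation follows recruitment of each cohort without saying whether clinics or patients are meant. If patients were enrolled after allocation by unblinded staff, a forced common baseline could introduce bias.

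**Conclusion.** The point holds as one of precision and conditional bias. As written, the Aim 2 model does not use the equality of baseline means that the Section 5 sequence provides, and no other text supplies that adjustment.

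The size cannot be taken from the documents. Under the assumed ranges the large-sample variance reduction is about 1% to 31%, or up to about 17% in SE. It is largest when clinic means correlate weakly between visits, and close to nil when they are very stable or when baseline SBP is tightly truncated. For illustration, if the planned analysis had 80% power at two-sided 5%, power would become about 0.90 at r = 0.5, 0.86 at r = 0.7 and 0.82 at r = 0.9, before the small slope-estimation cost.

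The conclusion rests on baseline being measured before allocation, and on an adjusted model with adequate covariance.

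**What to change.** In Analysis for Aim 2, make the arm contrast in SBP at 12 months the primary estimate, with time categorical, and pre-specify one of:

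1. Regression of 12-month SBP on arm, patient baseline SBP and clinic-mean baseline SBP, with a random clinic effect.
2. A constrained longitudinal model: categorical time plus arm-by-post-baseline-time terms, no arm main effect, an explicit within-patient covariance, and clinic and clinic-by-time random effects. State which visits enter.

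The constraint should not be added to the clinic-only random effect alone. Before adopting option 2, confirm from enrolment dates that every patient's baseline precedes the clinic's randomisation; if it does not, do not impose the common baseline mean. Take baseline SBP out of the reach of the change-in-estimate rule.

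The cost is a short edit to the analysis plan, made before the analysts are unblinded, and a slightly more complex model.

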All 30 HIV clinics enrolled will begin the study as part of the pre-implementation phase for 12 months, after which they will be randomly assigned to either the PF intervention (N=15) or the self-directed condition (N=15). Once randomized, the PHCs will participate in the 12- month implementation phase (intervention period) followed by a 12-month post- implementation period to assess its sustainability.

Randomization will occur in 5 cohorts of 6 PHCs every 6 months for 30 months and will be stratified by cohort to ensure balance over time. Upon completion of recruitment for each cohort, the clinics will be randomized in a 1:1 ratio to either the PF intervention or self-directed condition (i.e. receipt of information on TASSH implementation without PF). The sequence of randomization will be generated by [name], and kept in secure electronic format inaccessible to study sites, in accordance with CONSORT guidelines. Sites will be

informed of their randomization group by telephone. Because of the nature of the intervention, it is impossible to blind the patients, lay health advisors, and the study coordinators to the group assignment. The data analysts will remain blinded to treatment assignment until the completion of the implementation phase, defined as the period from baseline to 12-month follow-up(primary endpoint). During the post-implementation phase, the practice facilitators will leave the intervention sites and will have minor direct influence on the TASSH adoption. As the intervention concludes, data analysts will be unblinded following the primary endpoint. Preliminary database containing baseline and 12-month follow-up data will be locked upon unblinding for analysis.

Study intervention compliance (Group A).

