This aim will assess the extent to which inner setting variables (e.g., implementation leadership, implementation climate, and organizational culture) affect the degree of adoption of TASSH as defined in Aim 3, and its sustainability at 24 months. Particular attention will be paid to the pathways via which this occurs. We will estimate a just-identified path model using the robust weighted least squares estimator to investigate relationships among the theoretical mediators of implementation climate, implementation leadership, organizational culture, organizational readiness to change, and external change agent support. Based on our conceptual model, we will test the direct effects from the theoretical constructs to the adoption components (individually). In addition to the direct effects, the indirect effects from each variable to adoption via inner setting variables will be estimated as the product of component direct effects and tested using bootstrapped 95% confidence intervals. Finally, we will estimate the direct effects of the

predicted model of adoption on SBP reduction. Predicted probabilities of the adoption and sustainability outcomes and SBP will be calculated from path model coefficients to elucidate the magnitudes of direct and indirect effects.

Methods for handling missing data:

Although we will attempt to retain as high a fraction of participants as possible, we acknowledge that some attrition is likely, leading to missing outcome values. The generalized linear mixed models proposed for the primary and secondary analyses incorporate an assumption of data that are missing at random (MAR), meaning that the likelihood of a value being missing depends on observable characteristics (e.g., sex or age). In sensitivity analyses, we will assess the impact of different assumptions about the missing data mechanism, and will determine the robustness of trial results to these different assumptions. We will consider the use of multiple imputations of missing data as an alternative sensitivity analysis.

SECTION 7: Ethical Consideration

Institutional Review Board Approvals for this study will be obtained from the NYU School of Medicine (NYU) and the Nigerian Institute of Medical Research (NIMR).

Informed consent

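### The primary SBP model leaves covariate adjustment to an open rule that nothing fixes before unblinding, and it omits the randomisation cohort

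*Combined protocol and SAP*

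**What the plan says.** The primary outcome is change in SBP from baseline to 12 months. Section 6, Analysis for Aim 2, specifies a repeated-measures mixed model "with fixed effects for time and intervention arm, and random effects for clinic". It adds an arm-by-time term and reads the treatment effect from it: "this interaction, if non-zero, will indicate that the degree of change of SBP over time differs". The next sentence says that "assessments will include whether adjustment for any baseline characteristics is necessary, including such adjustments based on the change-in-estimate criteria". It lists no candidate covariates and gives no threshold, no order of selection and no form of entry (main effect or by time).

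On randomisation, Section 4 says that allocation of clinics "will be stratified by cohort to ensure balance over time", in five cohorts of six. Section 5 places it after baseline: "After completion of the baseline data collection, all HIV clinics will be randomized in 5 cohorts of 6 clinics every 6 months". Cohort appears in no analysis model, whether in the Protocol Summary, Aim 2 or Aim 3.

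On timing, Section 4 says "As the intervention concludes, data analysts will be unblinded following the primary endpoint", and then "Preliminary database containing baseline and 12-month follow-up data will be locked upon unblinding for analysis". That fixes the data. No text fixes the model before that point.

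**The concern.** A change-in-estimate rule is a tool for choosing confounders. Clinics here are randomised, so chance imbalance is already allowed for in the standard error and the rule is not needed for validity. What it does do is leave several versions of the primary analysis open at a time when the analysts may know the allocation. A primary result that depends on which version was reported can be challenged, even if nothing improper was done.

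Two further gaps affect the same model. The stratum used in the randomisation is not carried into the analysis. The clinic random effect is also not said to cover change over time, and this decides whether the test of arm-by-time respects the clustering at all.

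**Working it through.** **Inputs from the documents.** 5 cohorts × 6 clinics = 30 clinics; 30 × 32 patients = 960; 1:1 allocation, so 3 v 3 clinics per cohort and 15 v 15 overall. The counts agree. The documents give no SD, ICC, effect size, power or cohort variation, so there is no stated power to reproduce.

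**Assumed inputs.** SD of SBP change 17 mmHg; ICC of change 0.03 (also 0.01 and 0.05); true effect 4.5 mmHg for power; two-sided 5% test.

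**1. Form of entry decides what the rule does.** With complete data, a baseline covariate entered as a main effect takes the same value at each visit and cancels from the patient's change. In a simulated two-visit trial the arm-by-time estimate was 0.8289 without covariates, 0.8289 with cohort and age as main effects, and 0.8424 with both entered by time. So under main-effect entry the rule selects nothing. With 15–30% covariate-dependent dropout, main-effect entry moved the estimate by 0.01–0.13 mmHg on average (largest 0.51).

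**2. Type I error from the covariate rule, by-time entry, no cohort effect** (3,000 null trials per setting, 5 or 10 covariates, Monte Carlo error about ±1 point):

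| Share of variance explained by covariates | Most favourable model picked, two-sided (nominal 5%) | Counting only results favouring PF (nominal 2.5%) |
|---|---|---|
| 0 | 5.3–6.2% | 2.8–3.1% |
| 0.1 | 8.6–9.1% | 4.2–5.0% |
| 0.3 | 10.5–11.1% | 5.1–6.0% |

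A 10% rule applied mechanically gave 3.3–5.3% across these settings. A separate simulation under somewhat different assumptions gave 0.1–4.2% for the mechanical rule and at most 9.9% for free choice. In it, even the mechanical rule gave a different significance verdict from the unadjusted model in 9–12% of trials with a true 0.25 SD effect. At cohort SD 3 mmHg, free choice gave 2.6–5.8% without a cohort term and 5.3–11.0% with one. Adding cohort alone therefore does not close the choice.

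**3. Omitting cohort, with clinic variation in change modelled.** Clinic variance is 0.03 × 17² = 8.67 and patient variance 0.97 × 17² = 280.33. The variance of a clinic mean change is 8.67 + 280.33/32 = 17.43, so the true SE is √((2/15) × 17.43) = 1.52. The 3 v 3 balance removes cohort differences from the arm contrast, so 1.52 holds whatever the cohort SD. Without a cohort term the reported SE is about √((2/15) × (17.43 + (6/7) × cohort SD²)), where 6/7 = (4/5) × (15/14). Approximate power is Φ((4.5 − 2.048 × reported SE)/1.52). For cohort SD 2 this is an SE of 1.67 and Φ(0.71) = 76%. Simulation (20,000 trials per setting):

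| Cohort SD (mmHg) | 0 | 1 | 2 | 3 |
|---|---|---|---|---|
| Type I error, no cohort | 5.0% | 4.5% | 3.4% | 2.4% |
| Power, no cohort | 81% | 80% | 76% | 69% |
| Power, with cohort | 81% | 81% | 81% | 80% |

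Type I error with cohort was 4.9–5.0%. SD 3 is extreme: its variance (9) equals the whole assumed clinic variance (8.67) and is added to it.

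**4. Clinic intercept only.**

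- *With a patient term*, the model SE is √(4 × 17²/960) = 1.097 against a true 1.524. The effective critical value is 1.96 × 1.097/1.524 = 1.41, which gives 15.8% (simulated 15.2–15.9%; 8.0–9.0% at ICC 0.01 and 21.3–22.2% at ICC 0.05).
- *Without a patient term*, the model variance is about 4(s₀² + s₁²)/960. The true variance is (2/15) × V × (0.03 + 0.97/32), with V = s₀² + s₁² − 2r·s₀·s₁. For s₀ = 9, s₁ = 20, r = 0.3: s₀² + s₁² = 481 and V = 373, so SE 1.42 against 1.73, z = 1.60, 10.9%. For s₀ = 17, s₁ = 15, r = 0.5: s₀² + s₁² = 514 and V = 259, so SE 1.46 against 1.44, z = 1.99, 4.7%. Simulation over this range gave 5.4–10.6%.

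Under an intercept-only model, cohort changes power by less than 0.5 point.

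**The case against.** The strongest reply is that the Aim 2 text first defines a model with no covariates and only then speaks of assessing whether adjustment is needed. That can be read as a supplementary check on an unadjusted primary analysis. The wording supports this reading as well as the other, so it stands. It makes the fix easier, because one sentence would settle it, but it does not remove the ambiguity.

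A reader might infer that the rule as written raises the false-positive rate. The calculations do not support that. Adjustment usually means main effects, which leave the estimate unmoved with complete data, and the rule does not select on significance. The 9–11% needs three things together: by-time entry, covariates that explain SBP change, and picking the most favourable model.

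A reader might also infer that analysts plan to choose covariates after seeing allocation. The documents say only when unblinding and data lock occur. They are silent on when the model is chosen.

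Nor does leaving out cohort bias the result. Stratification already balances cohorts 3 v 3, and at cohort SD 1–2 mmHg the loss is 1–5 points of power.

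Finally, Section 5 is not wholly clear that all patients are enrolled before their clinic is randomised: after placing baseline first, it describes patient identification and the baseline visit under procedures following randomisation. If some enrol later, differential recruitment becomes possible. An open covariate list would not be the answer to that either; named covariates would.

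**Conclusion.** The concern holds in a limited form. The covariate rule is unspecified, nothing ties it to a date before unblinding, and cohort is in no model. The harm from the rule is discretion over the primary result: no inflation if followed mechanically, roughly 9–11% type I error in an assumed worst case of free choice. The harm from omitting cohort is a conservative test and lost power, and only if clinic variation in change is modelled and cohorts differ in SBP change. The unstated scope of the clinic effect can matter more: with an intercept only, type I error at ICC 0.03 is about 5–11% without a patient term and 15–16% with one. Every size here rests on assumed SD, ICC, effect and cohort variation. The gaps in the text do not depend on those assumptions. This should be fixed, and it does not put the design in doubt.

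**What to change.** Before unblinding, name one primary model for Aim 2 in the SAP, stating:

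- the 12-month arm contrast as the effect;
- time as a factor, and which of the scheduled visits (baseline, 6, 12, 18, 24 months) enter;
- cohort and cohort-by-time;
- the within-patient covariance structure;
- a random clinic effect that includes clinic-by-time, not an intercept alone;
- a named small-sample degrees-of-freedom method suited to 30 clinics.

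If further covariates are wanted, list them with their form of entry. Age and sex are natural candidates, since the missing-data text already mentions them as examples. Label any model chosen by change-in-estimate as a sensitivity analysis only. Constraining baseline means to be equal across arms is not requested: over the assumed range it changed the SE by between 7% smaller and 2.5% larger.

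The cost is SAP wording. No new data are needed and 960 stands. Cohort uses 4 of 28 clinic-level degrees of freedom (critical t 2.048 to 2.064). If cohorts do not differ, simulated power goes from 80.8% to 80.5%.
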